### **Possible Benefits:**

There are substantial potential benefits of participation in this study. All participants may benefit from the pre intervention evaluation, which may detect unknown or inadequately treated medical problems. In addition, we expect fitness improvement in the participants, which confers secondary health benefits.

Potential benefits for adults who exercise include:

- improvement of physiologic indicators of health (e.g., balance, blood pressure);
- full or partial elimination of impairments in ability to do daily activities;
- improvement in mental and/or social health status;
- reduction of risk of falls and fall-related injuries;
- reduction in risk of mortality; and
- reduction in medical care costs.

Potential benefits for adults who participate in the exercise testing include:

- improved awareness of their cardiovascular fitness level;
- greater confidence in the knowledge of their cardiovascular fitness level;
- greater knowledge of their fitness changes and the relationship between those measures and their ADLs.
- improvement in mental and/or social health status;
- reduction of risk of falls and fall-related injuries;
- reduction in risk of mortality; and
- reduction in medical care costs

As a service to the participants, anatomic scans will be read by a qualified physician if unexpected abnormalities arise. The major benefit of the study is the advancement of scientific knowledge about brain systems. Such knowledge may one day be used to increase the efficiency of rehabilitation techniques after brain injury, and might even have some implications for the way we teach skilled movement or other functions to neurologically normal individuals.

Participants may be compensated (250 US dollars) for participation in the project. Additionally, participants will be allowed to retain the exercise cycle used for the intervention.

Healthy subjects will also be recruited via the Emory University Alzheimer Disease Research Center (ADRC) Registry. Written permission from all patients is recorded on a signed informed consent form before inclusion in the ADRC Registry. This consent requires that the patients be willing to complete detailed histories, undergo comprehensive neurological and neuropsychological evaluations on an annual basis; submit blood for ascertainment of genetic information and establishment of lymphoblastoid cell lines; and agree to be contacted regarding participation in research projects of Emory investigators.

The PI and the Research Coordinator(s) will be added to the ADRC Registry protocol (IRB #133-98). Following this, the ADRC request form will be filled out in order to identify an appropriate list of potential participants.

Additionally, participants may be recruited from word of mouth and via print advertisements.

Individuals will be provided a copy of the informed consent and will be scheduled for an orientation session that describes the study goals and provides an opportunity to go over the informed consent. The PI/Co-PI or their trained and qualified colleagues will go over and describe the consent in a private office of the PI/Co-PI.

## 7. Statistical Analysis

**Statistical Analysis for Specific Aim 1.** We will model each of the outcome measures in Aim 1 (upper extremity) jointly using a mixed linear model to determine whether the mean responses of the groups are significantly different across the time points. We expect that modeling the outcomes jointly, using subject as a random factor, will allow for some gains in power. Our fixed factors will be time, treatment group and their interaction. This model will enable us to estimate the overall effects of time and treatment, and most importantly, how the effects of treatment differ with time.

**Statistical Analysis for Specific Aim 2.** For each of the outcome measures in Aim 2 (changes in fMRI and TMS activity during unimanual tasks) we will use a mixed linear model to determine whether the mean responses of the groups are significantly different across the time points. Our fixed factors will be time, treatment group and their interaction. This model will enable us to estimate the overall effects of time and treatment, and most importantly, how the effects of treatment differ with time.

**Statistical Analysis for Specific Aim 3.** For each of the outcome measures in Aim 3 we will use a mixed linear model to determine whether the mean responses of the groups are significantly different across the time points. Our fixed factors will be time, treatment group and their interaction. This model will enable us to estimate the overall effects of time and treatment, and most importantly, how the effects of treatment differ with time. Level of interhemispheric inhibition will be characterized by proportion of ipsilateral motor cortex recruited during fMRI tasks, ipsilateral silent period in TMS, and level of diminution of MEP size in the interhemispheric inhibition protocol in paired-pulse TMS.

**Power Analysis and Sample Size.** We powered this study on the previous cross-sectional studies assessing interhemispheric communication and motor performance. These studies had large effect sizes (1.33 to 1.67) as aerobic activity was related to ipsilateral motor cortical activity. As the proposed work is an intervention, we have applied a conservative estimate of these effects based on previous work with behavioral performance training over a similar timeframe (Kornatz et al., 2005) and those in the neuroimaging literature (Erickson et al., 2011). Further, data from our ongoing CDA-1 pilot study has shown a somewhat linear relationship between VO2max and levels of interhemispheric inhibition. While this data does not provide enough information to enable us to estimate a required sample size under the mixed model that will be used in the final analysis, we can conservatively estimate the sample size assuming a two-sample t-test would be performed on the post-pre differences for each group. Under this simpler model, a sample size of 20 per group will give us an approximate effect size of .83 for the fMRI and TMS measures. While this effect sizes is relatively large, we will have more power under the mixed model that we actually will use to analyze the data. Equally important, from the standpoint of our sample size, is that the data gathered on the other outcome measures would be invaluable in fully powering future study. Lastly, based on the retention rates in previous exercise studies we anticipate a 20 percent

drop-out rate among groups. As such, we will plan to enroll 24 per group to reach the needed sample size of 20 per group.

The research staff will use REDCap issued through the Atlanta Veterans Health Care System. Only deidentified data will be entered into REDCap by VA credentialed research personnel to run data analysis.

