### *Measures for Specific Aim 1.*

#### **Motor performance**

1. *Fitness Level:* We will assess physical fitness level using a cycle ergometry assessment of maximal volume of oxygen consumption. This is described in detail below.
2. *Purdue Peg Board Task:* The Purdue Pegboard measures unimanual motor dexterity. The test consists of two parts: 1) placing pins in a column of holes and 2) an assembly task using three components (pin, washer, collar). The participant is asked to place as many items as possible in 30 or 60 seconds, respectively.
3. *Nine Hole Peg Board Task:* A standard dexterity assessment, this task asks participants to place and remove pegs on a nine-hole pegboard as quickly as possible.
4. *Pinch and Grip Strength:* FDI and hand strength will be assessed using standard dynamometer (JAMAR) squeeze tests.
5. *Coin rotation task:* Another dexterity assessment, this task asks participants to rotate a coin (U.S. nickel) as quickly as possible for 20 rotations.
6. *Halstead finger tapping:* The Halstead finger tapping test is a standard test for testing psychomotor speed. The participant is asked to press a lever attached to a counter as many times as possible in 10 second trials.
7. *Jebsen Taylor hand function test:* The Jebsen Taylor hand function test is a timed 7-part assessment of common motor abilities performed with the dominant hand.
8. *Hand steadiness test:* A standard occupation therapy test measuring hand steadiness over a brief time interval (10 seconds).
9. *Poffenberger Crossed-Uncrossed Difference Test:* The Poffenberger paradigm is a test of transcallosal transfer time during reaction time responses. This 200-trial test compares reaction time based on hand of response and spatial presentation of stimulus cue.
10. *Target force matching:* The target force matching task is similar to the anisometric FDI muscle training used in the behavioral intervention. A computer presents a target force marker and the participant's task is to match the cued lift load target and hold for a set period of time. EMG is of the FDI taken during this assessment.
11. *Motor tracking:* The motor tracking task is a computer based presentation of a stimulus (vertical bar) moving laterally. The participant is instructed to track the

movement of the stimulus using a computer cursor controlled by a touchpad input device.

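### The Aim 1 joint model lists no outcome term, common scale or common direction, so a uniform between-group difference on the motor tests can be cancelled, diluted or reversed

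*Combined protocol and SAP*

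**What the plan says.** Section 7, Statistical Analysis for Specific Aim 1, puts the upper-extremity tests into one model: "We will model each of the outcome measures in Aim 1 (upper extremity) jointly using a mixed linear model". The reason given is power: the plan expects that "modeling the outcomes jointly, using subject as a random factor, will allow for some gains in power". The fixed part is then listed: "Our fixed factors will be time, treatment group and their interaction". The target is an overall effect: "This model will enable us to estimate the overall effects of time and treatment, and most importantly, how the effects of treatment differ with time". The paragraphs for Aims 2 and 3 list the same fixed factors but describe a model for each outcome and do not use the word jointly.

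Section 5, Measures for Specific Aim 1, lists fitness level and ten upper-extremity tests. Some are counts, such as the Purdue Pegboard: "The participant is asked to place as many items as possible in 30 or 60 seconds, respectively". Others are speed tasks. For the nine-hole pegboard, "this task asks participants to place and remove pegs on a nine-hole pegboard as quickly as possible"; in the coin task the participant must "rotate a coin (U.S. nickel) as quickly as possible for 20 rotations". Section 5 also places the motor tests among the primary outcomes of Aim 1. Neither section standardises the tests, states a direction for each, or reverses any sign.

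**The concern.** A model with one group-by-time coefficient for several tests estimates an average of the test-specific differences in change. The average means something only if the tests share a scale and a direction, and these do not. Purdue counts, strength and tapping rise with improvement. Nine-hole, coin rotation and Jebsen Taylor fall with improvement if scored as times. For hand steadiness, the crossed-uncrossed difference, force matching and tracking, the plan does not say which way is better.

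Aim 1 compares two active trainings, so the relevant signal is a between-group difference in change. If one training is better by the same amount on every test, the pooled coefficient can still be near zero or have the wrong sign. The same happens to the pooled time effect, although the objectives expect dexterity gains from both trainings. This is the only analysis that Section 7 gives for Aim 1. If scaling and signs are chosen once data are in hand, the direction of the conclusion depends on the analyst.

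**Working it through.** **Plan's own figure.** Section 7 gives no power or sample-size figure for the Aim 1 joint model. Its 20 per group and effect size of 0.83 refer to the fMRI and TMS measures under a two-sample t-test. They are used below only as a group size and an illustrative effect.

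**Inputs from the plan.** Ten upper-extremity tests, counting one score per test: three better when higher, three better when lower if timed, four with no stated direction. Fixed factors are time, group and their interaction; subject is random; 20 per group.

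**Assumed, because the plan gives no values.** A uniform between-group difference d, between-test correlation 0.3 after alignment, pre-post correlation 0.5, one pre and one post visit, two-sided 5% level.

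**1. Pooled effect on an equal-SD scale.** With U tests better when higher and D better when lower, the shared coefficient is d(U−D)/(U+D).
- Six tests with a clear direction: d(3−3)/6 = 0 for any d.
- All ten, the four others lower-is-better: d(3−7)/10 = −0.4d.
- All ten, the four others higher-is-better: d(7−3)/10 = +0.4d.
- At d = 0.5 the range is −0.20 to +0.20; at d = 0.83 it is −0.33 to +0.33.

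No mix recovers d.

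**2. Raw units.** The coefficient is then d times the signed mean of the SDs. Assumed SDs are 2, 8, 6 (Purdue, strength, tapping) and 2, 3, 5 (nine-hole, coin, Jebsen Taylor), with assumed means 13, 30, 45, 20, 18, 45.
- Six tests, d = 0.83: 0.83 × (2+8+6−2−3−5)/6 = 0.83 raw units. With no outcome term, the spread of test means enters the residual. The mean of the means is 28.5 and their variance is 969.5/6 = 161.6, against an average within-test variance of 142/6 = 23.7. The residual is near 161.6 + 23.7 = 185.3, and the standard error near √(4 × 185.3/(20 × 6)) = 2.49. The ratio 0.83/2.49 is 0.33, and simulation gives 0% significant results.
- Adding a reaction-time score in ms (assumed mean 300, SD 40, lower better): 0.83 × (6−40)/7 = −4.0. The estimate is negative in 99% of runs and significant in 0%.
- Adding only an outcome intercept to that last case leaves the estimate at about −4.1, now significant in the wrong direction in 21% of runs. An outcome main effect alone is not a cure.

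**3. Significance on z-scored, unaligned tests, d = 0.5.** For a t-test on each subject's mean change, the variance of that mean is [0.3(U−D)² + 0.7 × 10]/100.
- Aligned: (30+7)/100 = 0.37; SE = √(2 × 0.37/20) = 0.192; 0.5/0.192 = 2.60; power about 72% by simulation.
- 3 of 10 higher-is-better: (4.8+7)/100 = 0.118; SE = 0.109; −0.20/0.109 = −1.84; about 44% significant in the wrong direction.
- 4 of 10: (1.2+7)/100 = 0.082; SE = 0.091; −0.10/0.091 = −1.10; about 19% in the wrong direction.
- 5 of 10: about 2.5% in each direction. At 6 or 7 of 10 the sign is right and the estimate is cut to 0.10 or 0.20.

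The random-intercept model as listed gives lower rates. About 22% (24% in a repeat simulation) are significant in the wrong direction at 3 of 10, and about 2.5% at 4 of 10. At 6 or 7 of 10 it also shows dilution, not reversal.

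**4. Aligned comparison.** For the six clear tests, z-scored and sign-aligned with d = 0.83, the same model estimates 0.83 and rejects in about 99% of runs. Unaligned, it estimates 0.00 and rejects in 0%.

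**The case against.** The best defence is that modelling outcomes jointly can mean a multivariate mixed model with separate effects per test and correlated responses. The fixed-factor sentence recurs under Aims 2 and 3, where it applies to one outcome at a time, so it may be shorthand. On that reading nothing cancels. A reader might then infer that the expected power gain is illusory either way. The documents do not support that. With complete data and the same covariates for every test, outcome-specific joint estimates equal the separate ones. But the plan expects dropout (10–15% in Section 6, 20% in Section 7), and correlated tests can recover some information from incomplete records. An omnibus test of the test-specific interactions is also unaffected by sign. So some gain is possible, limited to those two routes. Still, the plan lists no outcome-specific terms, omnibus test or Aim 1 multiplicity rule, and it aims at an overall effect.

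A second defence is that Aim 3 lists the same motor tests and analyses each outcome, so opposing signs should be visible there. That helps detection, but Aim 3 concerns the later split into exercise and no exercise and does not replace the Aim 1 contrast.

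**Conclusion.** The concern holds for the model as listed. On an equal-SD scale, a uniform difference d pools to zero over the six tests with a clear direction and to between −0.4d and +0.4d over all ten. This needs only the directions, with the three speed tests scored as times; it does not depend on correlations or sample size. On raw units the usual result is a lost effect, as illustrated with assumed means and SDs.

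A reader might infer that the plan is likely to declare a benefit as significant harm. The documents do not support that. The 44% figure belongs to a t-test on the mean of already z-scored tests at the extreme mix of 3 of 10. The listed model gives about 22% there and about 2.5% at 4 of 10, and the raw-unit illustration without an outcome term gives 0%. Four directions are unstated, so the actual mix is unknown. What stands is that the model can cancel, dilute or reverse a uniform difference, and that nothing written prevents it.

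**What to change.** In Section 7, Aim 1:
- Convert each test to a z-score with the pooled mean and SD at the assessment before the first training period. Reverse the sign where lower is better, and name the direction of each of the ten tests.
- Add outcome and outcome-by-time to the fixed factors. Use a shared group-by-time effect as the joint test, and outcome-by-group-by-time as the check that effects are similar across tests.
- State how scores from the same subject and visit are correlated, for example by a subject-by-visit random effect. A subject intercept alone does not represent the correlation between changes on different tests.
- Report each test in its own units beside the pooled result.

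Separate models per test with a stated multiplicity rule would also cure the problem. If outcome-specific effects were intended, list those terms and say how one Aim 1 conclusion is drawn from them.

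The cost is wording and a little programming, with no new participants, visits or data. The pooled effect is then in SD units, which is slightly harder to read clinically. The text should be settled before the Aim 1 data are analysed.

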*Research Design.* The proposed study will examine 40 older, sedentary Veterans from the greater Atlanta area. Participants will be randomly assigned to one of two 15-month intervention conditions involving aerobic fitness training and behavioral training. The study is a reversal design in which both groups are assessed pre-treatment with both fMRI and TMS measures, as well as behavioral measures at study enrollment. As part of the design, both groups will undergo a 3-month waiting period during which they will engage in an organized stretching routine with no aerobic exercise component. After this waiting period, the participants again undergo behavioral, fMRI and TMS assessments. At this point, the participants will be assigned to either a behavioral treatment group involving a motor coordination protocol previously shown to improve upper extremity motor performance in older adults (Christou et al, 2011) or a supervised aerobic training group at the Atlanta VA Medical Center. The design of the study is depicted in the in Figure 6 below. The primary outcomes of this aim are changes in fMRI and TMS measures of interhemispheric communication and motor performance tests.

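### The joint Aim 1 model names subject as its random factor but gives no test term and no covariance between tests or visits, so the group-by-time standard error can be wrong in either direction

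*Combined protocol and SAP*

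**What the plan says.** Section 7, Statistical Analysis for Specific Aim 1, sets one model for the whole battery: "We will model each of the outcome measures in Aim 1 (upper extremity) jointly using a mixed linear model". The only random term it names is subject ("using subject as a random factor"). The fixed part is also given: "Our fixed factors will be time, treatment group and their interaction". The section singles out the change of the treatment effect over time as its most important result.

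Nowhere does the document add a term for which test a score comes from, a common scale or direction, a subject-by-test or subject-by-visit effect, a residual covariance, or robust standard errors. The gain in power is stated as an expectation: "We expect that modeling the outcomes jointly, using subject as a random factor, will allow for some gains in power". Power Analysis and Sample Size, in the same section, again expects more power from the mixed model, but concedes that the available data do not allow a sample size to be estimated under it.

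**The concern.** A random subject intercept makes every pair of scores from one person equally correlated, whether they share a test, a visit or neither. Two plausible sources of variation are then pushed into the residual.

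- **Person by test.** The battery mixes strength, dexterity, tapping speed, steadiness and reaction time. Someone may be persistently good at one and poor at another. That difference cancels in a change score, but the model counts it as error, so the standard error is too large.
- **Person by visit.** Section 6 gives the dexterity evaluation as a single-day example. A good or bad day, or a person's own response to training, can move many tests together. That shift does not average out over tests, but the model treats it as if it did, so the standard error is too small.

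At stake is the p-value for the key Aim 1 comparison. It could miss a real difference between exercise and dexterity training, or declare a false one, and the plan does not show which is more likely.

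**Working it through.** **The plan's own figure.** There is none for this model. The effect size of 0.83 with 20 per group is stated for the fMRI and TMS measures under a two-sample t-test. At two-sided 5% (power and sidedness are not stated) it gives 72.5% power. It serves below only as a benchmark for a single test.

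**Inputs**
- Tests, K = 10. Measures for Specific Aim 1 has eleven numbered items, the last being motor tracking ("The motor tracking task is a computer based presentation of a stimulus"). Item 1 is fitness, not upper extremity: "We will assess physical fitness level using a cycle ergometry assessment of maximal volume of oxygen consumption".
- Assessments, T = 4: at enrolment ("as well as behavioral measures at study enrollment"), after the stretching period ("After this waiting period, the participants again undergo behavioral, fMRI and TMS assessments"), and after each of the two interventions. The fifth assessment closes the six-month Aim 3 phase.
- 20 per arm, from Power Analysis and Sample Size.
- Two-sided 5%: assumed, as Aim 1 has no stated level.
- Variance shares v_p (person), v_pt (person by test), v_pv (person by visit) and v_e (residual): assumed, as the documents give none. Tests are taken as standardised and aligned, with complete data.

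**Formulas.** For the arm difference in change from the second to the third assessment:
- true variance is proportional to v_pv + v_e/K;
- the random-intercept model uses v_r/K, with v_r = [T(K−1)v_pt + K(T−1)v_pv]/(KT−1) + v_e;
- R = model SE / true SE = √[(v_r/K)/(v_pv + v_e/K)], and type I error is about 2Φ(−1.96R).

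With K = 10 and T = 4, v_r = (36v_pt + 30v_pv)/39 + v_e. For the third row below, (36×0.35 + 30×0.10)/39 + 0.25 = 0.650, so R = √(0.0650/0.1250) = 0.72.

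| v_p, v_pt, v_pv, v_e | v_r/10 | v_pv + v_e/10 | R | 2Φ(−1.96R) | Simulated, contrast | Simulated, 3-df interaction |
|---|---|---|---|---|---|---|
| .30, .40, 0, .30 | 0.0669 | 0.0300 | 1.49 | 0.3% | 0.4% | 0.1% |
| .30, .40, .05, .25 | 0.0658 | 0.0750 | 0.94 | 7% | 7% | 8% |
| .30, .35, .10, .25 | 0.0650 | 0.1250 | 0.72 | 16% | 15% | 26% |
| .30, .30, .15, .25 | 0.0642 | 0.1750 | 0.61 | 24% | 24% | 41% |

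**Where the direction switches.** Setting v_r = K·v_pv + v_e gives T(K−1)v_pt = KT(K−1)v_pv, so v_pv = v_pt/K. With v_pt = 0.40 and ten tests, that is a person-by-visit share of 0.04.

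**Checks**
- Fitted mixed models (80 per case, 10 tests, 5 visits) gave a mean model SE of 0.116 against an empirical SD of 0.076 for shares .30, .40, 0, .30. For .30, .40, .10, .20 they gave 0.114 against 0.152.
- Counting the fifth assessment leaves R at 1.49 and 0.94 in the first two rows.
- With v_pt = v_pv = 0, R = 1.00 and type I error is about 5%.
- Analysing one average score per person per visit gave about 5% throughout.
- On raw scales with no test term (test means assumed to differ with an SD of 3), type I error was 0 to 0.13%.

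**Power of a valid joint test.** Take an effect of 0.83 SD of one test's change. With ρ = v_pv/(v_pv + v_e), the average of ten changes has variance ρ + (1−ρ)/10 relative to one test. An effect common to all ten then has size 0.83/√[ρ + (1−ρ)/10]. For the last row, ρ = 0.15/0.40 = 0.375 and the size is 0.83/√0.4375 = 1.25, giving 97% power. For the first row, ρ = 0 and the size is 2.62, giving nearly 100%. If only 3 of the 10 tests respond, these sizes are multiplied by 0.3 (0.38 and 0.79), and power is 21% and 68%, below the 72.5% for one responsive test.

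**The case against.** Four points can be made for the plan.

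1. **A reader might infer that subject is declared the only random factor.** The text says subject is a random factor. It does not say the only one, nor intercept only. Joint modelling is compatible with a multivariate mixed model that has test-specific subject effects. This stands: the plan under-specifies its model and does not declare a wrong one. But the model that can be fitted from the words given is the one examined here.
2. **A reader might infer that the standard error is wrong.** The documents support only that it can be. It is right if both extra components are zero, or if they cancel near v_pv = v_pt/10. The second row of the table is already close to nominal.
3. **A reader might infer that the power gain is illusory.** The calculation above does not bear that out: a correctly specified test of a shared effect gains substantially. The gain depends on two conditions the plan does not state, a shared effect and a modelled covariance. With separate effects per test, an unstructured covariance and complete data, no single test gains anything.
4. **The inflated error rates assume tests on a common scale, which the plan does not promise.** This is fair. On raw scales with no test term, inflation gives way to extreme conservatism. The literal model then fails differently, so the point is not removed.

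It is also true that the sample size rests on the fMRI and TMS measures and not on this model. However, the Aim 1 Research Design lists motor performance tests among the primary outcomes.

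**Conclusion.** The point holds as a gap in specification with real consequences for the test's error rate. Run as written on standardised tests, the group-by-time test can have a type I error from well below to several times its nominal 5%: 0.4% to 24% for the change over the first intervention, and 0.1% to 41% for the 3-df interaction.

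The algebra is firm. The size of the error in this trial is not known, because every variance share is an assumption. The figures also assume complete data and 20 per arm. The pattern does not depend on the choice of four or five assessments. The power gain has not been shown, and for an effect confined to a few tests a joint test can lose power.

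**What to change.** Settle the following in section 7 before any analysis.

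1. State how each test is standardised, and reverse signs so that higher is better on all of them. List the scores that enter, leaving fitness out.
2. Choose one model:
   - (a) average the aligned tests to one score per person per visit, and fit time, group and their interaction to it with an unstructured visit covariance; or
   - (b) keep the joint model, adding a test fixed effect, person-by-test and person-by-visit random effects, and Kenward-Roger degrees of freedom.

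   A fully unstructured 40 × 40 matrix (40×41/2 = 820 parameters) is not an option with 40 people.
3. State that the test is of an effect common to all tests.
4. Replace the power sentence with one saying that a gain is expected only if the effect is shared across tests and the covariance is modelled, and that no mixed-model power has been calculated.

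The cost is SAP wording only; design and data collection do not change. There are two downsides. If person-by-visit variation is material, the valid standard error may be larger than hoped. An average also dilutes an effect confined to a few tests.
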